#### 5. METHODS

### 5.1. Study endpoints

### 5.1.1. Main ventilator settings and parameters

The main study endpoint is a set of key ventilation settings and ventilation parameters, including tidal volume (VT); peak inspiratory pressure (PIP); plateau pressure (Pplat); positive end-expiratory pressure (PEEP); fraction of inspired oxygen (FiO2); inspiration to expiration ratio (I:E); inspiration time; set and total respiratory rate (RR); compliance (Crs); driving pressure ( $\Delta P$ ); and the mechanical power of ventilation (MP).

### 5.1.2. Secondary ventilation settings and parameters

Secondary parameters are type of ventilatory support; type of airway management; type of ventilation mode; saturation of peripheral oxygen (SpO2); end-tidal carbon dioxide (EtCO2) and only if available blood gas analysis.

### 5.1.3. Clinical outcomes

The clinical outcomes involve the incidence of Pediatric Acute Respiratory Distress Syndrome (PARDS); number of ventilation-free days at day 28; duration of ICU stay; ICU mortality and cause of death.

#### 5.2. Data to be collected

All data to be collected are part of standard clinical care.

#### 5.2.1. Patient characteristics

- Age (weeks or months);
- Sex (male or female);
- Height (cm);
- Weight (kg); and
- Gestational age (weeks).

## 5.2.2. Medical status

- Comorbidities (pulmonary, cardiac, neuromuscular, syndrome/genetic abnormalities, oncologic, organ transplant, chronic ventilation, mental retardation);
- Reason of ventilatory support; and
- Pediatric Risk of Mortality (PRISM) or Pediatric Index of Mortality (PIM) score, depending on which scoring system is used in the Pediatric Intensive Care Unit (PICU).

### 5.2.3. Data collection at day of intubation

(note that this could also be the day of admission to a pediatric ICU if transferred from another hospital with mechanical ventilation)

- Date of ICU admission; and
- Date and time of intubation (if the patient is transferred from another hospital than day 0 is the day of admission).

### 5.2.4. Daily data collection

(this is for the first three full calendar days in the pediatric ICU)

At start of ventilation or at arrival when the patient has been intubated in another hospital, ventilation data will be collected directly and after 1 hour (name 'day 0'). Thereafter, ventilation data will be collected daily at a time point in the morning representing a steady state overnight, e.g., before the first morning blood gas is drawn, up to day 3, or the day of extubation or death.

- Type of ventilatory support: invasive ventilation; noninvasive ventilation (NIV), high–frequency oscillatory ventilation (HFOV), continuous positive airway pressure (CPAP), bi-level positive airway pressure (BiPAP), and high–flow nasal oxygen (HFNO);
- Type of airway management: intubation or tracheostomy (invasive); nasal/facial mask (non-invasive);
- Ventilation mode: volume controlled ventilation (VCV), assist-control (AC) or synchronized intermittent mandatory ventilation (SIMV); pressure controlled ventilation (PCV), AC or SIMV; volume support ventilation (VSV); pressure support ventilation (PSV); synchronized intermittent mandatory ventilation (SIMV) ± pressure support (PS); pressure regulated volume control (PRVC); neurally adjusted ventilatory assist (NAVA); NIV; HFOV; (n)CPAP; BIPAP; and HFNO;
- Ventilator settings: including but not restricted to: expiratory tidal volume (VTe) (mL) or inspiratory tidal volume (VTi) (mL) (only in case VTe is not available); PEEP (cm H2O); PIP (cm H2O) or Pplat (cm H2O) (cm H2O); level of pressure support above PEEP (cm H2O); trigger (flow or pressure, if flow then rate set); FiO2 (%); set and measured RR; I:E ratio; or inspiration time; SpO2 (%); EtCO2 (kPa);
- Arterial blood gas (ABG) analysis results or capillary blood gas (CBG) analysis results, only if available: pH; partial pressure of oxygen (PaO2) (kPa or mmHg); partial pressure of carbon dioxide (PaCO2) (kPa or mmHg);

- Imaging: X-ray (y/n). If yes, the first available X-ray after start of mechanical ventilation, will be assessed by the researcher (to prevent inter-observer variability) whether new opacities (unilateral or bilateral) consistent with acute pulmonary parenchymal disease are seen which are not due primarily to atelectasis or pleural effusion (y/n);
- Treatment: undergoing veno-venous, veno-arterial or arterio-venous extracorporeal membrane oxygenation (ECMO) (y/n); use of sedative (y/n) if yes: continue or bolus; use of neuromuscular blocking agents (NMBA) (y/n); if yes: continue or bolus; use of opiates (y/n); if yes: continue or bolus; use of vasoactive drugs (y/n); if yes: continue or bolus; and use of prone positioning.

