#### Main study endpoints

The primary endpoint is a set of key ventilation settings and ventilation parameters, including tidal volume (VT), peak inspiratory pressure (PIP), plateau pressure (Pplat), positive end-expiratory pressure (PEEP), inspired fraction of oxygen (FiO2), inspiration to expiration ratio (I:E), inspiration time, set respiratory rate, total respiratory rate, compliance (Crs), driving pressure ( $\Delta$ P) and the mechanical power of ventilation (MP). Secondary endpoints include the incidence of PARDS, duration of ventilatory support, the number of days free from ventilatory support at day 28, length of ICU stay, and ICU mortality. We will also determine whether there are potentially modifiable factors that have an independent association with outcome.

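### Daily data collection asks for PIP or Pplat, but the main endpoint names both and adds three measures that must be derived from recorded pressures

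*Protocol*

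**What the plan says.** Protocol section 5.1.1 lists the items of the main endpoint. The pressures appear as separate entries: "peak inspiratory pressure (PIP); plateau pressure (Pplat); positive end-expiratory pressure (PEEP". The same list includes "compliance (Crs); driving pressure" "and the mechanical power of ventilation (MP". The summary, under Main study endpoints, repeats the separation: "peak inspiratory pressure (PIP), plateau pressure (Pplat), positive end-expiratory pressure (PEEP".

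Section 5.2.4 says what is recorded at each time point. For airway pressure above PEEP the entry is "PIP (cm H2O) or Pplat (cm H2O) (cm H2O". It gives no order of preference, no rule by ventilation mode and no item stating which pressure was recorded. Compliance, driving pressure and mechanical power are not named in that section.

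Two other features of the same bullet bear on the point. It opens with "Ventilator settings: including but not restricted to", so it is not a closed list. For tidal volume it does rank the alternatives: the inspiratory value is taken "only in case VTe is not available".

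Section 7.1 points to complete-case analysis where data are missing. Section 2.1 sets out to describe practice, changes over time and geo-economic differences, and to find modifiable factors associated with outcome. Section 7.3 relates predefined ventilation settings and parameters to outcome.

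**The concern.** An endpoint that names two pressures cannot be filled reliably from an instruction to record one of them. If a site follows the wording and enters only PIP, the Pplat item is missing for that patient, and driving pressure and compliance can be formed only as dynamic values from PIP minus PEEP. These include resistive pressure whenever flow continues at end-inspiration. If a site enters only Pplat, the derived values are static and the PIP item is missing.

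The choice is left to the site, so it could follow ventilation mode or local habit. Part of any difference between centres, regions or years could then reflect what was written down rather than how children were ventilated, and those differences are what the study sets out to describe. The association analyses are exposed in the same way. Section 1.2 names driving pressure and mechanical power among the parameters associated with outcome in adults, so they are likely to be of interest here.

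The point belongs in the protocol because an analysis plan can choose formulas but cannot recover a pressure that was never recorded.

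**Working it through.** The protocol gives no figure on this point to reproduce. The check compares its sections and then illustrates the size under stated assumptions.

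**Endpoint against collection list**

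- PIP: named in the main endpoint (5.1.1 and summary); collected only as an alternative to Pplat (5.2.4).
- Pplat: named in the main endpoint; collected only as an alternative to PIP.
- PEEP: named and collected.
- Driving pressure, compliance, mechanical power: named in the main endpoint and absent from the collection list, so they must be derived.
- Ventilation mode: collected in detail (5.2.4).

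A PIP-only or Pplat-only record therefore satisfies the collection wording but leaves one endpoint item empty. It also fixes which version of the derived items is possible.

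**Illustration**

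The protocol gives neither typical pressures nor formulas. The assumed inputs are PEEP 5 cmH2O, Pplat 18 cmH2O, and PIP above Pplat by 0, 3 or 5 cmH2O. The assumed definitions, with P being Pplat or PIP, are:

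- driving pressure = P − PEEP
- compliance = VT / (P − PEEP)

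From Pplat, driving pressure is 18 − 5 = 13. From PIP in the same patient:

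| PIP − Pplat | PIP | Driving pressure | Change from 13 | Compliance ratio | Change |
|---|---|---|---|---|---|
| 0 | 18 | 13 | 0% | 13/13 = 1.00 | 0% |
| 3 | 21 | 16 | +23% | 13/16 = 0.81 | −19% |
| 5 | 23 | 18 | +38% | 13/18 = 0.72 | −28% |

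Tidal volume cancels in the compliance ratio.

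A second set of assumptions shows how the result moves: PEEP 6, Pplat 20, gap 0 to 8 cmH2O. Driving pressure goes from 14 to 14–22 (0% to +57%), and compliance changes by 0% to −36% (14/22 = 0.64). With a simplified mechanical power proportional to RR × VT × P, the change is 0% to +40% (28/20 = 1.40).

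In both sets the difference is nil when PIP equals Pplat. It therefore varies with the patient and the breath, and no constant offset would correct it.

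**The case against.** The strongest counter-argument is that the case report form is not shown and the list in 5.2.4 is expressly open. The form may already hold both pressures, and the wording may be loose drafting. The unit is printed twice after Pplat, and the same bullet offers I:E ratio or inspiration time although the main endpoint names both. This stands in part: the protocol does not forbid recording both pressures, and one should not infer that the form accepts only one. But nothing requires both. The I:E comparison is also weak, because inspiration time and respiratory rate together give the I:E ratio, whereas neither PIP nor Pplat can be calculated from the other.

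A reader might also infer that PIP and Pplat will be pooled into one variable. No section says so. If they are entered as labelled values, complete-case analysis fits the loss of patients without Pplat at least as well as substitution of PIP. The firm consequence is possible missing values. A mixture is a possibility only.

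The absence of formulas for driving pressure, compliance and mechanical power is not a defect here, since an analysis plan that is not shown may supply them. Mode is already recorded, so analysis by mode is possible.

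Finally, all data come from standard care (5.2) and collection is deliberately minimal (summary, Study design). Where Pplat was never measured, no rewording will produce it. This stands, and it limits what the fix can gain to patients in whom both values exist.

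**Conclusion.** The collection wording in 5.2.4 does not match the main endpoint in 5.1.1 and the summary. Followed literally, it can leave PIP or Pplat unrecorded in a patient. Driving pressure, compliance and mechanical power could then rest on different pressures across patients or drop out under complete-case analysis, and some of the variation between centres, regions or years could be a product of recording.

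Under the first set of assumptions (PEEP 5, Pplat 18, gap 0 to 5 cmH2O), PIP-based driving pressure is 0% to 38% higher and compliance 0% to 28% lower than the Pplat-based values. The gap is assumed and zero is within its range, so the upper figures should not be read as typical. The documents do not support the stronger statement that the main endpoint will be a biased mixture. The sample size is unaffected. The change is worth making before data collection because it is cheap and a pressure left unrecorded may not be recoverable later.

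**What to change.** In section 5.2.4, replace the either/or entry with two separate fields: PIP and, where measured in routine care, Pplat (measured / not available). Each value then identifies itself, and the list matches 5.1.1 and the summary. Add a sentence that PIP-based (dynamic) and Pplat-based (static) derived values will be kept distinguishable and reported separately. The formulas, including the one for mechanical power, can be left to the analysis plan. No new mode field is needed. If the case report form already has both fields, only the protocol wording has to change.

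The cost is one extra entry when both values exist, with no added procedure. The downside is that fewer patients will contribute Pplat-based values, and which patients have them will still depend on local practice.

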### 5.2.5. Follow-up

Outcome data will be collected at ICU discharge:

- PARDS (y/n), according to the 2023 Pediatric Acute Lung Injury Consensus Conference (PALICC) definition (24);
- Air leak during ICU stay;
- Intubated (y/n), and if not, extubation date;
- Successful extubation; defined as no reintubation within 48 hours after extubation (y/n), if not: reason of reintubation;
- Alive (y/n), and if not, date of death in ICU; cause of death;
- Number of ventilation-free days at day 28 (zero in case of death or start ECMO);
- Date of discharge from ICU; and
- Destination after ICU discharge (other ICU, ward or home).

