#### 2. OBJECTIVES & HYPOTHESES

#### 2.1. Objectives

The aims of this study are to:

- describe the practice of ventilatory support;
- study temporal changes in practice of ventilatory support;
- study geo–economic differences in ventilatory support and outcomes in critically ill pediatric patients; and
- identify potentially modifiable factors that have independent associations with outcome including duration of ventilatory support, the number of days free from ventilatory support at day 28, length of ICU stay, and ICU mortality.

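### Ventilation-free days are defined at day 28, but outcomes are recorded only up to ICU discharge, so the score can be too high after early discharge and cannot be computed after transfer while intubated

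*Protocol*

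**What the plan says.** Section 2.1 names "the number of days free from ventilatory support at day 28" among the outcomes for the modifiable-factor aim, next to duration of support, length of ICU stay and ICU mortality. Section 5.1.3 lists it again as a clinical outcome.

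Section 5.2.5 then fixes what is collected. It opens with "Outcome data will be collected at ICU discharge", and these items follow under that heading:

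- **Ventilation status:** "Intubated (y/n), and if not, extubation date".
- **Vital status:** "Alive (y/n), and if not, date of death in ICU; cause of death".
- **The endpoint:** "Number of ventilation-free days at day 28 (zero in case of death or start ECMO").
- **Where the child went:** "Destination after ICU discharge (other ICU, ward or home").

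The bedside ventilation record cannot fill the gap, because section 5.2.4 limits it: "this is for the first three full calendar days in the pediatric ICU". Section 7.1 expects little or no loss to follow-up and points to complete-case analysis where data are missing.

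**The concern.** The endpoint looks 28 days ahead, but observation stops when the child leaves the ICU. For any child who leaves before day 28, the score has to be filled in for a period that nobody recorded. Two groups are affected in different ways.

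- **Discharged to the ward or home:** the child keeps all remaining days as ventilation-free, whatever happens next. The error goes one way only, towards too many days.
- **Transferred to another ICU while intubated:** the score is not computable. Under complete-case analysis these children would drop out, and still being ventilated is itself related to outcome.

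The second group also touches ICU mortality, because the child is recorded as alive at the only outcome time point although intensive care continues.

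Section 2.1 also plans to compare outcomes between geo-economic settings. If discharge and transfer practice differs between those settings, part of an observed difference could reflect where observation stopped. An analysis plan cannot repair this later, because the missing status would never have been recorded, and the study is meant to run for 10 years.

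**Working it through.** **Is day-28 status available anywhere?**

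| Needed for the day-28 score | What is collected | Gap |
|---|---|---|
| Death by day 28 | Alive or not at ICU discharge; date of death in ICU (5.2.5) | Death on the ward, at home or in a receiving ICU |
| ECMO start by day 28 | ECMO yes/no in the daily record, which ends at day 3 (5.2.4); zero-score rule applied at ICU discharge (5.2.5) | ECMO after discharge or transfer |
| End of ventilation | Extubation date, only if not intubated at discharge (5.2.5) | No date for a child who leaves intubated |
| Renewed ventilation by day 28 | Reintubation within 48 hours of extubation (5.2.5) | Renewed support after ICU discharge |

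No section provides a day-28 contact, follow-up after transfer, or a scoring rule for children who leave early. Children who stay in the ICU through day 28 are not affected.

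**Per-child size.** The protocol gives no formula. I take the score as 28 minus the day of extubation.

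- Extubated day 4, discharged day 6, ward death day 12: recorded 28 − 4 = 24; by definition 0.
- Extubated day 10, discharged, death by day 28: recorded 28 − 10 = 18; by definition 0.
- Transferred intubated on day 5: at most 28 − 5 = 23 if extubated at once, at least 0. No value can be derived.

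**Effect on the mean.** Overstatement = share with an unobserved zero-scoring event × days wrongly credited. The protocol gives no such share. Assume that 0.5% to 2% of children die after ICU discharge by day 28, and use 18 and 24 credited days from the examples above.

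| Assumed share | 18 days credited | 24 days credited |
|---|---|---|
| 0.5% | 0.09 | 0.12 |
| 1% | 0.18 | 0.24 |
| 2% | 0.36 | 0.48 |

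The range is roughly 0.1 to 0.5 days. Unobserved ECMO or renewed ventilation would add to it; transferred children are not in this figure.

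**ICU mortality.** Only ICU-to-ICU transfers matter here. Deaths missed = patients × share transferred × mortality after transfer. Both rates are assumptions. In the 3,300 patients of section 4.4:

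- 1% transferred, 3% mortality: 3,300 × 0.01 × 0.03 ≈ 1 death.
- 10% transferred, 20% mortality: 3,300 × 0.10 × 0.20 = 66 deaths.

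A range this wide shows only that the size cannot be settled from the protocol.

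**Sample size.** The protocol's own figure reproduces closely (100 events ÷ 0.03 = 3,333, against 3,300 stated) and does not change.

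**The case against.** The best case for leaving the plan alone has several parts.

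- **Secondary endpoint, low-burden study.** The main endpoint is the set of ventilation settings and parameters, which this does not touch, and the protocol deliberately keeps data collection small. This stands, and it limits the weight of the point. It does not remove the mismatch, since days free from support at day 28 is a named outcome of an aim and of a hypothesis.
- **Transfers are already identifiable.** The destination field includes another ICU, so they can be reported separately without new data. This also stands, and the fix uses it. But identifying these children does not supply their missing scores.
- **Linking records between ICUs is not cheap.** Section 9.1 restricts identifying data to local investigators. This stands, so linkage is not asked for.

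Some stronger readings are tempting, but the document does not support them.

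- A reader might infer that the protocol classes transferred children as survivors. No sentence says so. What follows from the fields is that they are recorded as alive at the only outcome time point.
- A reader might infer that a child liberated early who dies in the ICU after day 28 must score zero. The parenthesis qualifies a day-28 quantity, and the date of ICU death is collected, so such a child can be scored correctly.
- A reader might set post-discharge deaths against the expected ICU deaths. Ward and home deaths lie outside ICU mortality by definition, so they bear on ventilation-free days only.
- A reader might infer that a transferred child enters the study twice. That would need a participating receiving ICU, the same collection period and more than 12 further hours of support. It is a separate question.

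**Conclusion.** The point holds for children who leave the ICU before day 28. As section 5.2.5 is written, their ventilation-free days can be too high, and for those transferred while intubated they cannot be computed. In one child the error can be most of the scale (24 recorded against 0). On the cohort mean it is roughly 0.1 to 0.5 days if 0.5% to 2% die after ICU discharge by day 28. That share is an assumption, so the true size is unknown. The effect on ICU mortality is confined to ICU-to-ICU transfers and is also unknown.

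A reader might go further and conclude that centres or regions with early discharge will look better. The protocol has no discharge, transfer or regional figures, so a bias that differs between settings is a possibility and not a finding. The sponsor should correct the mismatch, because data not collected now cannot be recovered later.

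**What to change.** In section 5.2.5, for each child who leaves the ICU before day 28:

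1. Record from the hospital record the vital status and ventilatory-support status, with dates, at day 28 or hospital discharge, whichever comes first.
2. State that a child discharged from hospital alive and off support is assumed to remain so to day 28.
3. Report ICU-to-ICU transfers as their own category. Give a sensitivity analysis for ventilation-free days and for ICU mortality, with best and worst case for those transferred while ventilated, in place of dropping them as incomplete. For a transfer on day 5 the two ends for ventilation-free days are 23 and 0.

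If no extra data are wanted, rename the endpoint *ventilation-free days to day 28, observed to ICU discharge* and keep the transfer sensitivity analysis.

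The first option costs a few extra eCRF items from the hospital record and rests on the assumption in item 2. The second costs only wording and analysis, at the price of a less ambitious endpoint. Neither needs records to be linked between hospitals.

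### The end of invasive ventilation is dated only by extubation, so for a child ventilated through a tracheostomy the duration of support and the liberation curve end too early or cannot be dated

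*Protocol*

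**What the plan says.** Section 5.2.4 lists two invasive airways as alternatives: "Type of airway management: intubation or tracheostomy (invasive); nasal/facial mask (non-invasive"). This item belongs to the daily form, of which the protocol says "this is for the first three full calendar days in the pediatric ICU"; collection runs "up to day 3, or the day of extubation or death".

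Section 5.2.3 asks for "Date and time of intubation". Section 5.2.5, completed at ICU discharge, then asks for:

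- "Intubated (y/n), and if not, extubation date";
- "Successful extubation; defined as no reintubation within 48 hours after extubation (y/n), if not: reason of reintubation";
- "Number of ventilation-free days at day 28 (zero in case of death or start ECMO").

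The follow-up list has no item for tracheostomy, for ventilator status at discharge, or for the date on which ventilation ended. The destination item distinguishes only another ICU, the ward or home.

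Two planned results need an end-of-ventilation time. Duration of ventilatory support is a secondary endpoint in the Summary and an outcome in sections 2.1 and 2.2. Section 7.2 plans Kaplan–Meier curves for liberation from the ventilator.

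**The concern.** The daily form and the follow-up form do not use the same idea of invasive support. In the daily form it can run through a tube or a tracheostomy. In the follow-up form its end is marked only by removal of the tube. For most children the two dates coincide. They come apart for a child whose tube is replaced by a tracheostomy while ventilation continues, and for a child who never had a tube because a tracheostomy was already in place.

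Children converted during the stay and still ventilated afterwards have long durations of support. If their end date is the day of conversion, long durations are recorded as shorter ones, and a continuing course of ventilation appears as a liberation event. If sites differ in whether they count a tracheostomy tube as intubation, the same course is recorded differently in different places. A statistical analysis plan could define how to derive the outcomes, but it could not supply a date or an airway status that was never collected. The study is planned to run for 10 years, so the gap would run through the whole dataset.

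**Working it through.** The protocol states no figure on this point, so there is none to reproduce. The check applies the items as written to three courses; the days are examples.

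**Course 1: tube on day 0, tracheostomy on day 14, still ventilated at day 28.**

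| Item or outcome | Items read literally | Actual course |
|---|---|---|
| Intubated at ICU discharge | no | invasively ventilated to day 28 or beyond |
| Extubation date | day 14 | tube removed, ventilation continues |
| Successful extubation | yes, if no reintubation within 48 hours | not liberated |
| Duration from the dated items | 14 − 0 = 14 days | at least 28 days |
| Liberation curve | event on day 14 | no event by day 28 |
| Ventilation-free days | entered separately, derivation not stated | 0 |

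For conversion on day *t* with ventilation continuing at day 28, the duration lost up to day 28 is 28 − *t*:

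- day 7: 28 − 7 = 21 days;
- day 14: 28 − 14 = 14 days;
- day 21: 28 − 21 = 7 days.

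**Course 2: existing tracheostomy, ventilated for 5 days.** Section 5.2.4 places day 0 at the start of ventilation, so the start can be located even without an intubation time. No tube is removed, so the extubation date is blank and duration cannot be calculated from the dated items. The site could still enter 28 − 5 = 23 ventilation-free days if the child survives without ECMO or further ventilation. No recorded date would confirm that entry.

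**Course 3: conversion after day 3.** The daily airway item has stopped and the follow-up form does not ask about tracheostomy. The conversion cannot be found afterwards, so course 1 cannot be told apart from a true extubation on day 14.

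**Conditional illustration for ventilation-free days.** Suppose a site counts these days from the extubation date, which the protocol does not say. Suppose also that a share *p* of children is converted on day *t* and still ventilated at day 28. The mean is then overstated by *p* × (28 − *t*). Both *p* and *t* are assumptions, because the protocol gives no tracheostomy rate or timing.

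| Assumed share | Day 7 | Day 14 | Day 21 |
|---|---|---|---|
| 1% | 0.01 × 21 = 0.21 | 0.01 × 14 = 0.14 | 0.01 × 7 = 0.07 |
| 2% | 0.02 × 21 = 0.42 | 0.02 × 14 = 0.28 | 0.02 × 7 = 0.14 |
| 5% | 0.05 × 21 = 1.05 | 0.05 × 14 = 0.70 | 0.05 × 7 = 0.35 |

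Under the same assumed shares, mean duration counted to day 28 would be understated by the same amounts. That statement needs the literal reading of the extubation item, but no assumption about how ventilation-free days are entered.

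**The case against.** The strongest reply is that the literal reading is not the only one. Section 5.2.4 ends daily collection for every child at extubation or death, although its airway list includes tracheostomy and mask. That suggests extubation is loose shorthand for the end of support, and a site might well treat a tracheostomy tube as intubation. Data collection is kept minimal on purpose, section 5.4 plans a pilot to find problems, and section 9.2 relies on standard operating procedures in which field instructions could sit. This stands in part: the result is ambiguity, not certain misclassification of every such child. It does not remove the point, because the protocol leaves the reading to the site and nothing else collected after day 3 reveals which one was used.

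It is also fair that successful extubation is not among the listed endpoints, and that the main endpoint (ventilation settings) and ICU mortality are untouched. The effect lies on duration and the liberation curve, and on the ability to check ventilation-free days.

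A reader might infer three stronger things, and the documents support none of them.

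- *That a converted child is necessarily credited with false ventilation-free days.* That outcome is an item of its own and is not tied to the extubation date; a site can correctly enter 0.
- *That a child with an existing tracheostomy drops out of the complete-case analysis of section 7.1.* The start is anchored in section 5.2.4 and ventilation-free days are entered separately. Only a duration calculated from dates is lost.
- *That the geo-economic comparison is shown to be biased.* The protocol says nothing about how tracheostomy rates or timing vary between centers or regions. Inconsistent recording is a risk to that comparison, not a demonstrated bias.

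**Conclusion.** The point holds as a gap in the outcome items. Under the protocol's own airway categories, the dated items cannot represent invasive ventilation that continues through a tracheostomy. For a converted child the literal result is a duration up to day 28 that is too short by 28 − *t* days, a false liberation event and a false successful extubation. For a child with an existing tracheostomy, duration cannot be calculated from the dated items. For ventilation-free days the accurate statement is narrower: there is a rule for death and ECMO but none for tracheostomy, and the entry cannot be checked against a dated end of ventilation.

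The per-child figures rest on the literal reading and on ventilation continuing at day 28. No effect on the whole study can be derived from the protocol. The range of 0.07 to 1.05 days in mean ventilation-free days depends on counting from extubation and on an assumed share of 1% to 5%, so it shows scale only. The number of children is probably limited, but the change is cheap and the data cannot be recovered later from the form, so it should be made.

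**What to change.** - **Section 5.2.5, end of ventilation.** Replace the intubation and extubation-date item with: *Invasively ventilated through tube or tracheostomy at ICU discharge (y/n); if not, date invasive ventilation ended.*
- **Section 5.2.5, new item.** Add: *Tracheostomy placed during ICU stay (y/n, date).*
- **Derivation.** State that duration of invasive ventilation, liberation and ventilation-free days are derived from the end-of-ventilation date. A child still invasively ventilated at ICU discharge has no such date: treat duration and the curve as censored at discharge, and state the rule for ventilation-free days.
- **Successful extubation.** State that tube removal for conversion to a tracheostomy does not count.
- **Section 5.2.3.** For children who arrive with a tracheostomy, record the start of invasive ventilation in place of the intubation time.

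The cost is two reworded eCRF items and one added tracheostomy item with its date, all available from the chart at ICU discharge. The planned pilot is a natural place to test the wording.
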